#### Superficial basal cell carcinoma:

##### Clinical efficacy:

The efficacy of imiquimod 5 times per week for 6 weeks was studied in two double-blind vehicle controlled clinical trials. Target tumours were histologically confirmed single primary superficial basal cell carcinomas with a minimum size of 0.5 cm^2 and a maximum diameter of 2 cm. Tumours located within 1 cm of the

eyes, nose, mouth, ears or hairline were excluded. In a pooled analysis of these two studies, histological clearance was noted in 82% (152/185) of patients. When clinical assessment was also included, clearance judged by this composite endpoint was noted in 75% (139/185) of patients. These results were statistically significant ( $p < 0.001$ ) by comparison with the vehicle group, 3% (6/179) and 2% (3/179) respectively. There was a significant association between the intensity of local skin reactions (e.g. erythema) seen during the treatment period and complete clearance of the basal cell carcinoma.

Five -year data from a long-term open-label uncontrolled study indicate that an estimated 77.9% [95% CI (71.9%, 83.8%)] of all the subjects who initially received treatment became clinically clear and remained clear at 60 months.

#### Actinic keratosis:

##### Clinical efficacy:

The efficacy of imiquimod applied 3 times per week for one or two courses of 4 weeks, separated by a 4 week treatment-free period, was studied in two double-blind vehicle controlled clinical trials. Patients had clinically typical, visible, discrete, nonhyperkeratotic, nonhypertrophic AK lesions on the balding scalp or face within a contiguous 25 cm^2 treatment area. 4-8 AK lesions were treated. The complete clearance rate (imiquimod minus placebo) for the combined trials was 46.1% (CI 39.0%, 53.1%).

One-year data from two combined observational studies indicate a recurrence rate of 27% (35/128 patients) in those patients who became clinically clear after one or two courses of treatment. The recurrence rate for individual lesions was 5.6% (41/737). Corresponding recurrence rates for vehicle were 47% (8/17 patients) and 7.5% (6/80 lesions). The rate of progression to squamous cell carcinoma (SCC) was reported in 1.6% (2/128 patients).

There are no data on recurrence and progression rates beyond 1 year.

##### Paediatric patients:

The approved indications genital warts, actinic keratosis and superficial basal cell carcinoma are conditions not generally seen within the paediatric population and were not studied.

Aldara Cream has been evaluated in four randomised, vehicle controlled, double-blind trials in children aged 2 to 15 years with molluscum contagiosum (imiquimod n = 576, vehicle n = 313) . These trials failed to demonstrate efficacy of

imiquimod at any of the tested dosage regimens (3x/week for  $\leq$  16 weeks and 7x/week for  $\leq$  8 weeks).

[Go to top of the page](#)

## 5.2 Pharmacokinetic properties

External genital warts, superficial basal cell carcinoma and actinic keratosis:

Less than 0.9% of a topically applied single dose of radiolabelled imiquimod was absorbed through the skin of human subjects. The small amount of drug which was absorbed into the systemic circulation was promptly excreted by both urinary and faecal routes at a mean ratio of approximately 3 to 1. No quantifiable levels ( $>5$  ng/ml) of drug were detected in serum after single or multiple topical doses.

Systemic exposure (percutaneous penetration) was calculated from recovery of carbon-14 from [ $^{14}\text{C}$ ] imiquimod in urine and faeces.

Minimal systemic absorption of imiquimod 5% cream across the skin of 58 patients with actinic keratosis was observed with 3 times per week dosing for 16 weeks. The extent of percutaneous absorption did not change significantly between the first and last doses of this study. Peak serum drug concentrations at the end of week 16 were observed between 9 and 12 hours and were 0.1, 0.2, and 1.6 ng/mL for the applications to face (12.5 mg, 1 single-use sachet), scalp (25 mg, 2 sachets) and hands/arms (75 mg, 6 sachets), respectively. The application surface area was not controlled in the scalp and hands/ arms groups. Dose proportionality was not observed. An apparent half-life was calculated that was approximately 10 times greater than the 2 hour half-life seen following subcutaneous dosing in a previous study, suggesting prolonged retention of drug in the skin. Urinary recovery was less than 0.6% of the applied dose at week 16 in these patients.

Paediatric patients:

The pharmacokinetic properties of imiquimod following single and multiple topical application in paediatric patients with molluscum contagiosum (MC) have been investigated. The systemic exposure data demonstrated that the extent of absorption of imiquimod following topical application to the MC lesional skin of the paediatric patients aged 6-12 years was low and comparable to that observed in healthy adults and adults with actinic keratosis or superficial basal cell carcinoma. In younger patients aged 2-5 years absorption, based on  $C_{\text{max}}$  values, was higher compared to adults.

[Go to top of the page](#)

### 5.3 Preclinical safety data

Non-clinical data revealed no special hazard for humans based on conventional studies of safety pharmacology, mutagenicity and teratogenicity.

In a four-month rat dermal toxicity study, significantly decreased body weight and increased spleen weight were observed at 0.5 and 2.5 mg/kg; similar effects were not seen in a four month mouse dermal study. Local dermal irritation, especially at higher doses, was observed in both species.

A two-year mouse carcinogenicity study by dermal administration on three days a week did not induce tumours at the application site. However, the incidences of hepatocellular tumours among treated animals were greater than those for controls. The mechanism for this is not known, but as imiquimod has low systemic absorption from human skin, and is not mutagenic, any risk to humans from systemic exposure is likely to be low. Furthermore, tumours were not seen at any site in a 2-year oral carcinogenicity study in rats.

Imiquimod cream was evaluated in a photocarcinogenicity bioassay in albino hairless mice exposed to simulated solar ultraviolet radiation (UVR). Animals were administered imiquimod cream three times per week and were irradiated 5 days per week for 40 weeks. Mice were maintained for an additional 12 weeks for a total of 52 weeks. Tumours occurred earlier and in greater number in the group of mice administered the vehicle cream in comparison with the low UVR control group. The significance for man is unknown. Topical administration of imiquimod cream resulted in no tumour enhancement at any dose, in comparison with the vehicle cream group.

[Go to top of the page](#)

## 6. PHARMACEUTICAL PARTICULARS

[Go to top of the page](#)

### 6.1 List of excipients

isostearic acid  
benzyl alcohol  
cetyl alcohol  
stearyl alcohol  
white soft paraffin  
polysorbate 60

sorbitan stearate  
glycerol  
methyl hydroxybenzoate (E218)  
propyl hydroxybenzoate (E216)  
xanthan gum  
purified water.

[Go to top of the page](#)

#### 6.2 Incompatibilities

Not applicable.

[Go to top of the page](#)

#### 6.3 Shelf life

2 years.

[Go to top of the page](#)

#### 6.4 Special precautions for storage

Do not store above 25°C.

Sachets should not be re-used once opened.

[Go to top of the page](#)

#### 6.5 Nature and contents of container

Boxes of 12 or 24 single-use polyester/aluminium foil sachets, containing 250 mg of cream.

Not all pack sizes may be marketed.

[Go to top of the page](#)

#### 6.6 Special precautions for disposal and other handling

No special requirements.

[Go to top of the page](#)

### 8. MARKETING AUTHORISATION NUMBER(S)

EU/1/98/080/001-002

[Go to top of the page](#)

**9. DATE OF FIRST AUTHORISATION/RENEWAL OF THE AUTHORISATION**

Date of first authorisation: 18/09/1998

Date of last renewal: 03/09/2008

[Go to top of the page](#)

**10. DATE OF REVISION OF THE TEXT**

April 2010

3.1 List of Abbreviations

AE	Adverse Event
AK	Actinic Keratosis
ATC	Anatomical Therapeutic Chemical
BCC	Basal Cell Carcinoma
CCTP	Consolidated Clinical Trial Protocol
CI	Confidence Interval
CM	Concomitant Medication
DK	Denmark
FAS	Full Analysis Set
ICH	International Conference on Harmonisation
LSR	Local Skin Response
MedDRA	Medical Dictionary for Regulatory Activities
PP	Per Protocol
PT	Preferred Term
SCC	Squamous Cell Carcinoma
SD	Standard Deviation
SE	Standard Error
SMQ	Standardised MedDRA Query
SOC	System Organ Class
WHODD	WHO Drug Dictionary

4 Statistical Analysis Plan Authors

PPD [REDACTED], M.Sc., Principal Statistician, Biostata Aps, [name], tel: PPD [REDACTED], e-mail: PPD [REDACTED]

PPD [REDACTED], PhLic, Senior Clinical Project Manager, Trial Execution, LEO Pharma A/S, [name], tel: PPD [REDACTED], e-mail: PPD [REDACTED]

PPD [REDACTED]; MS, PhD (cand), Senior Medical Writer, Pharma IT, [name]; tel: PPD [REDACTED], e-mail: PPD [REDACTED]

PPD [REDACTED], MD, PhD, Associate Research Fellow, Medical Department, LEO Pharma A/S, [name], tel: PPD [REDACTED], e-mail: PPD [REDACTED]

5 Introduction

The statistical analysis will be performed as outlined in the Consolidated Clinical Trial Protocol (CCTP). This Statistical Analysis Plan contains a more technical and detailed elaboration of some points in the statistical analysis section in the CCTP.

6 Trial Analysis Sets

The full analysis set (FAS) is defined as all randomised subjects.

The safety analysis set is defined as all subjects who receive an initial study treatment and have safety data available.

The per protocol (PP) analysis set will be used as safety and efficacy subsets and is defined as subjects in the FAS who complete the trial without major protocol deviations affecting the primary and secondary safety and efficacy endpoints. Censoring as well as a full exclusion from the PP analysis set will be used in the primary analysis and in all other time-to-event analyses. A subject who is to be excluded from the PP analysis set will be in the analysis until the subject is censored at the time the event leading to exclusion from PP occurs in time-to-event analyses in case the event occurs after Day 1. This is in line with estimands defined by the composite strategy in ICH E9 (R1) addendum on estimands (1).

Please see the Analysis Set Definition Document for details.

7 Statistical Analysis

Please see section [7.5](#) for general principles.

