## 10 INVESTIGATIONAL PLAN

### 10.1 TRIAL DESIGN

#### 10.1.1 Overall Design

This is a phase 4, multi-centre, randomised, two-arm, open label, active-controlled, parallel group, 36-month trial.

All subjects who qualify for this trial are to have 5 to 9 clinically typical, visible and discrete AK lesions (confirmed by histopathology of one of the AKs prior to randomisation) within a contiguous 25 cm^2 treatment area on the face or scalp. This area of skin will be referred to as the selected treatment area.

In case of baldness or partial baldness, the forehead should be defined by the previous hairline.

Subjects will be randomised in a 1:1 ratio to the following treatment arms:

- Arm A: Ingenol mebutate gel 0.015% applied daily for 3 consecutive days to the selected treatment area followed by 8 weeks' rest. Retreatment for another 3 consecutive days if the treatment field is not completely cleared of AKs at Week 8
- Arm B: Imiquimod 5% cream applied 3 days per week for 4 weeks to the selected treatment area followed by 4 weeks' rest. Retreatment for 4 weeks if the treatment field is not completely cleared of AKs at Week 8.

Study visits will take place at Screening (Visit 1), during the treatment period on Days 1 and 4, Weeks 2, 4 and 8 (Visits 2 to 6) for initial treatment and, if retreatment is required, on Week 8+3 days and Weeks 10, 12, and 16 (Visits 7 to 10). During the Follow-up period visits will take place at Week 20 and Months 12, 18, 24, 30 and 36 (Visits 11 to 16).

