### **10.10.1 Subject Qualification for Analysis**

All subjects for whom a signed informed consent is obtained and a CRF is started will be accounted for in the study report.

Efficacy analyses will be based on the Full Analysis Set (FAS), which is defined as all randomized subjects. Safety analyses will be based on the Safety Analysis Set, which is defined as all subjects who receive an initial study treatment and have safety data available.

---

A per protocol (PP) analysis set will be used as safety and efficacy subsets and will be defined as subjects in the FAS who complete the trial without major protocol deviations. The composition of the PP analysis set will be determined and documented in reviews of the study database. The safety and efficacy analyses based on the PP analysis set will be performed to support the results obtained for the primary and secondary safety and efficacy endpoints.

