7.3.1 Censoring

Since the primary and secondary safety criteria are time-to-event analyses, a censoring scheme will be defined. This is not detailed in the CCTP.

Subjects from the safety analysis set will be included in the time-to-event analyses, as described in [Table 1](#):

Table 1: Censoring

Event	Date	Outcome
SCC	Date of biopsy	Event
Missing result from a biopsy	Date of biopsy	Censored
Trial completion without SCC	Date of last visit with assessment and no SCC	Censored
Trial discontinuation	Date of last visit with assessment and no SCC	Censored
Death from any cause	Date of death	Censored

SCC: Squamous cell carcinoma

In addition, a PP censoring will be defined, which is censoring at the time when a subject is excluded from the PP analysis set, as described in [Table 2](#):

Table 2: PP censoring

Event	Date	Outcome
Exclusion from PP analysis set with no documented SCC	Date of last visit with assessment before exclusion with no SCC	Censored

PP: Per protocol, SCC: Squamous cell carcinoma

Details on censored subjects are given by subject ID in the analysis set definition document.

Trial ID: LP0041-63	Date: 28-AUG-2019	Version: Final 1.0 Page 10 of 32
---------------------	--------------------------	-------------------------------------

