7.4 Analysis of Efficacy

All efficacy analyses will be carried out for the FAS and the PP analysis set unless otherwise stated.

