7.5.6 Changes to the Protocol

- The CCTP states: “*An interim analysis of trial data, obtained when approximately half of the trial period has elapsed, will be conducted. Assuming the time schedule shown in section 10.2, this will be prepared 3 years after study start. The interim analysis will not impact the conduct of this trial.*” This interim analysis was not conducted since the Pharmacovigilance Risk Assessment Committee at the European Medicines Agency found that the Periodic Safety Update Report was satisfactory.
- The CCTP states: “*A per protocol (PP) analysis set will be used as safety and efficacy subsets and will be defined as subjects in the FAS who complete the trial without major protocol deviations.*” Only deviations having impact on safety or efficacy will be considered. As the primary analysis is a time-to-event analysis, subjects will be censored from the PP analysis at the time of the deviation, i.e. the subject will be in the PP analysis set until the day when the deviation takes place.
- To support the primary endpoint, descriptive statistics of demographic and other baseline characteristics will be presented for the safety analysis set and not for the FAS as described in the CCTP.
- Reason for premature discontinuation from treatment is not presented as it is not captured in the eCRF. Reason for not applying trial medication according to protocol is listed.

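### As written, the per-protocol set requires completion of the 36-month trial, so the supportive PP clearance analyses can lose subjects for events after the clearance assessment; SAP sections 6 and 7.5.6 need reconciling

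*SAP*

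**What the plan says.** Protocol 10.10.1 introduces one PP set for both safety and efficacy, which "will be defined as subjects in the FAS who complete the trial without major protocol deviations". SAP section 6 repeats this and limits the deviations to those bearing on the primary and secondary endpoints, taken together: the set "is defined as subjects in the FAS who complete the trial without major protocol deviations affecting the primary and secondary safety and efficacy endpoints". Protocol 10.1.1 gives the length: "This is a phase 4, multi-centre, randomised, two-arm, open label, active-controlled, parallel group, 36-month trial".

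SAP section 6 then gives relief for late exclusions. A subject due for exclusion stays in the analysis until censored, but only "in time-to-event analyses in case the event occurs after Day 1". SAP 7.3.1 gives the mechanism: "In addition, a PP censoring will be defined, which is censoring at the time when a subject is excluded from the PP analysis set". Its Table 2 sets the censoring date for the SCC analyses.

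SAP 7.5.6 lists the PP definition as a change to the protocol: "As the primary analysis is a time-to-event analysis, subjects will be censored from the PP analysis at the time of the deviation". The same sentence goes on to explain that the subject belongs to the PP set up to the day of the deviation.

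For efficacy, SAP 7.4 states: "All efficacy analyses will be carried out for the FAS and the PP analysis set unless otherwise stated". The endpoints are binary: complete and partial clearance after the last cycle (Week 8 or 16), and complete clearance sustained through Month 12. Protocol 10.10.4 compares them by a stratified Cochran-Mantel-Haenszel (CMH) analysis. SAP Appendix I lists six PP efficacy tables: 3-2 and 3-8 by visit, 3-4 and 3-10 after the last cycle, and 3-6 and 3-12 at Month 12.

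**The concern.** A clearance outcome is fixed at its assessment. If PP membership also depends on what the subject does afterwards, the PP clearance rate is conditioned on later events that say nothing about adherence during treatment. Censoring cannot help, because a CMH analysis of a binary response either counts a subject or does not.

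The filter on deviations does not remove the problem. It covers all primary and secondary endpoints jointly, so a deviation at Month 24 that matters only for the 3-year SCC endpoint would, on the literal wording, also remove a valid Week 8 result.

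Late exclusion could plausibly be related to clearance. Protocol 5.3 and 8.3 expect some or many subjects to need further treatment because neither product is universally effective. Cross-over between the two products in the field stays prohibited to Month 36 (Protocol 10.1.2 and 10.6.11). Subjects with persistent or recurrent lesions are more exposed to such later deviations, and the trial is open label. At stake is whether the PP results can do the job Protocol 10.10.1 gives them, which is to support the secondary efficacy results.

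**Working it through.** **The plan's own figure.** The only design calculation is the precision statement in Protocol 10.3. With 240 per arm, p + 1.96 × √(p(1 − p)/240) gives 2.26% at p = 1.0% and 4.475% at p = 2.5%, which match the stated 2.26% and 4.48%. It concerns the SCC rate and does not bear on this point. Only the 240 per arm is carried forward.

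**Time from assessment to trial completion**, with the SAP's 30.4375 days per month:
- Week 8: 36 − 56/30.4375 = 34.2 months
- Week 16: 36 − 112/30.4375 = 32.3 months
- Month 12: 36 − 12 = 24 months

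**Which rule applies where**

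| Analysis | Completion required by SAP 6? | Relief for later events? |
|---|---|---|
| PP time to SCC or neoplasia | Yes | Yes, PP censoring |
| PP clearance (CMH and by visit) | Yes | None in SAP 6; 7.5.6 unclear |
| FAS clearance | No | Not needed |

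**Illustration of size.** The documents give no clearance, dropout or deviation rate, so every rate here is an assumption. Let c be true clearance, and let d₁ and d₀ be the late-exclusion proportions among cleared and non-cleared subjects:

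PP clearance = c(1 − d₁) / [c(1 − d₁) + (1 − c)(1 − d₀)]

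With c = 0.50 and 240 in the arm:
- d₁ = 0.10, d₀ = 0.20: 0.45/0.85 = 52.9%, on 204 subjects
- d₁ = 0.10, d₀ = 0.30: 0.45/0.80 = 56.25%, on 192 subjects
- d₁ = d₀ = 0.10: 0.45/0.90 = 50.0%, no bias

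Clearance ratio when the truth is 1.00:
- same selection in both arms: 52.9/52.9 or 56.25/56.25 = 1.00
- selection in one arm, loss unrelated to clearance in the other: 52.9/50 = 1.06 to 56.25/50 = 1.125
- selection in one arm but reversed (20% to 30% of cleared and 10% of non-cleared lost): 0.40/0.85 = 47.1% and 0.35/0.80 = 43.75%, so 0.94 to 0.875

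**Precision when loss is unrelated to outcome.** The 95% half-width for a difference at 50% per arm is 1.96 × √(2 × 0.25/n). With n = 240 it is 8.95 points. Late exclusion of 5%, 10%, 20% and 30% leaves 228, 216, 192 and 168 per arm, with half-widths of 9.18, 9.43, 10.00 and 10.69 points.

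**The case against.** The best counter-argument is SAP 7.5.6. It cites the protocol's completion-based definition, announces a change to it, and describes membership as ending on the day of the deviation. On that reading a subject who deviates at Month 24 was still in the set at Week 8 and Month 12. This stands as a possible reading. It does not settle the matter, because the stated reason is the time-to-event primary analysis, binary endpoints are not mentioned, and section 6 keeps the completion requirement.

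A reader might also infer that anyone who moves away or dies in year 3 will certainly be removed from the Week 8 result. The documents do not support that as fact. SAP 7.5.6 and the planned table of PP exclusions (Table 1-5) refer only to deviations, and discontinuation and death sit in the ordinary censoring table (SAP 7.3.1, Table 1). Exclusion for withdrawal or death rests on the words about completing the trial alone.

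The Analysis Set Definition Document, to which the SAP defers, is not among the documents and may hold endpoint-specific rules. Shell 12, footnote 4, shows that the SAP can state an exclusion specific to a clearance endpoint, but no such limit on later events appears there.

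Finally, 1.125 should not be read as an expected bias. It needs strong selection in one arm and none in the other, which nothing in the documents supports. The direction is open too: repeat treatment with the assigned product is allowed from Week 20, which may give uncleared subjects a reason to stay.

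**Conclusion.** The point holds as a defect of definition. Taken literally, SAP section 6 and Protocol 10.10.1 make PP clearance at Week 8/16 and Month 12 depend on events up to 24 to 34 months later. SAP 7.5.6 either contradicts this or leaves it unclear.

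The consequence is limited. Efficacy is a secondary objective, the PP analyses are supportive, the FAS clearance results are untouched, and the PP time-to-event analyses keep each subject's earlier follow-up through censoring. A reader might conclude that the efficacy findings as a whole are biased; the documents do not support that.

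The size is unknown. Under the assumed 50% clearance and late exclusion of 10% of cleared and 20% to 30% of non-cleared subjects, PP clearance shifts by 2.9 to 6.25 points. The ratio moves from 1.00 to between 1.06 and 1.125 only if the selection is confined to one arm. Loss unrelated to clearance costs precision and nothing else. The practical harm is that a difference between PP and FAS results could not be attributed to adherence in the treatment period.

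**What to change.** In SAP section 6, remove the completion requirement for the efficacy endpoints. Define PP membership by relevant major deviations up to and including the assessment analysed:
- **Tables 3-4 and 3-10:** Week 8, or Week 16 if retreated.
- **Tables 3-6 and 3-12:** Month 12.
- **Tables 3-2 and 3-8:** each visit in turn. Flags for Week 8/16 and Month 12 alone would leave Week 20 and Months 18 to 36 undefined.

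State that withdrawal, death or deviation after that assessment does not exclude the subject from it. Keep PP censoring unchanged for the time-to-event analyses. Reword 7.5.6 so that it says how time-limited membership applies to binary endpoints and to withdrawal, and align the Analysis Set Definition Document.

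The cost is a few lines of text and some extra PP flags. The deviation dates are already needed for PP censoring, so no new data are required.
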